5.2 INCLUSION CRITERIA

To be eligible for the trial, subjects must meet all of the following criteria:

- 1) Patients undergoing ablation of sustained atrial tachycardia (post AF ablation) using 3D mapping.
- 2) Age range 18-85yrs.
- 3) Signed informed consent

5.3 EXCLUSION CRITERIA

Subjects with any of the following will be excluded from the study:

- 1. Patients with typical flutter.
- 2. Patient with non-sustained atrial tachycardia
- 3. Contraindication to catheter ablation
- 4. Unable to give informed consent

5.4 WITHDRAWAL CRITERIA

If patients lose the capacity to consent or wish to withdraw voluntarily, then they will be excluded from the study from this point. If the patient has agreed on the consent form, any data collected up to this point will be included in the data analysis.

6. ADVERSE EVENTS

6.1 DEFINITIONS

Adverse Event (AE): any untoward medical occurrence in a patient or clinical study subject. **Serious Adverse Event (SAE):** any untoward and unexpected medical occurrence or effect that:

Results in death

Is life-threatening – refers to an event in which the subject was at risk of death at the time of the event; it does not refer to an event which hypothetically might have caused death if it were more severe

Requires hospitalisation, or prolongation of existing inpatients' hospitalisation Results in persistent or significant disability or incapacity Is a congenital anomaly or birth defect

Medical judgement should be exercised in deciding whether an AE is serious in other situations. Important AEs that are not immediately life-threatening or do not result in death or hospitalisation but may jeopardise the subject or may require intervention to prevent one of the other outcomes listed in the definition above, should also be considered serious.

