6.2 REPORTING PROCEDURES

All adverse events will be reported. Depending on the nature of the event the reporting procedures below will be followed. As the patients are undergoing clinically indicated procedures any questions concerning adverse event reporting will be directed to the main clinical departmental lead and clinician supervising the case in the first instance.

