6.2.1 Non serious AEs

All such events, whether expected or not, will be recorded.

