6.2.2 Serious AEs

A SAE form should be completed and faxed to the Chief Investigator within 24 hours. However, relapse and death due to non-cardiac conditions, and hospitalisations for elective treatment of a pre-existing condition do not need reporting as SAEs.

[figure not shown]
All SAEs should be reported to the <name of REC> where in the opinion of the Chief Investigator, the event was:

'related', ie resulted from the administration of any of the research procedures; and unexpected', ie an event that is not listed in the protocol as an expected occurrence reports of related and unexpected SAEs should be submitted within 15 days of the Chief Investigator becoming aware of the event, using the NRES SAE form for non-IMP studies. The Chief Investigator must also notify the Sponsor of all SAEs.

Local investigators should report any SAEs as required by their Local Research Ethics Committee, Sponsor and/or Research & Development Office.

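### Section 6.1 makes unexpectedness part of the SAE definition while section 6.2.2 uses it as a later filter, so a recognised serious complication of ablation need not trigger prompt SAE reporting

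*Combined protocol and SAP*

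**What the plan says.** Section 6.1 gives two definitions. An adverse event is "any untoward medical occurrence in a patient or clinical study subject", with no condition on expectedness. A serious adverse event is "any untoward and unexpected medical occurrence or effect that" has one of the listed outcomes: death, threat to life, new or prolonged hospital stay, lasting disability, or congenital anomaly. A closing paragraph lets medical judgement extend the term serious to important events that fall short of those outcomes. It does not mention expectedness.

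Section 6.2 opens with "All adverse events will be reported" and refers to the procedures that follow. There are two:

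- Section 6.2.1, non-serious events: "All such events, whether expected or not, will be recorded".
- Section 6.2.2, SAEs: "A SAE form should be completed and faxed to the Chief Investigator within 24 hours", and "The Chief Investigator must also notify the Sponsor of all SAEs". SAEs that the Chief Investigator considers both related and unexpected also go to the ethics committee within 15 days. Unexpected is explained there as "an event that is not listed in the protocol as an expected occurrence".

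Section 6.2.2 also exempts some events from SAE reporting: relapse, non-cardiac death, and elective admission for a pre-existing condition. Complications of ablation are not among them.

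**The concern.** Seriousness concerns the outcome of an event. Expectedness concerns whether the event was foreseen. Section 6.1 merges the two by making unexpectedness a condition of being an SAE at all. Every participant undergoes catheter ablation, which has recognised complications. On a literal reading, a site may decide that such a complication was foreseeable and therefore not an SAE, even if it was life-threatening or prolonged the hospital stay.

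What is at stake is the fast reporting route: the 24-hour form, the Chief Investigator's opinion on relatedness, and notice to the Sponsor. All three depend on the event being an SAE.

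**Working it through.** The plan gives no figure on this point and no arithmetic applies. The check is to follow one event through sections 6.1 to 6.2.2. Take a complication of ablation that prolongs the hospital stay and that the site regards as a known risk.

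1. **Is it an adverse event?** Yes. That definition in 6.1 has no expectedness condition.
2. **Does it have a listed serious outcome?** Yes, prolonged hospitalisation.
3. **Is it an SAE?** That depends on what unexpected means in 6.1, which does not define the word or refer forward to 6.2.2.
4. **Does the medical-judgement paragraph bring it back in?** Not clearly. That paragraph is for situations other than the listed outcomes. Because it carries no expectedness condition, a lesser event could count as serious while an expected life-threatening one does not.
5. **Is there another route?** Section 6.2 says that all adverse events are reported, but gives no deadline or recipient of its own. Section 6.2.1 covers expected events only if they are non-serious, and asks only that they be recorded.

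The result under each way of reading 6.1:

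| Reading of unexpected in 6.1 | Is the event an SAE? | 24-hour form and Sponsor notice | What the unexpected filter in 6.2.2 does |
|---|---|---|---|
| The site's own view of known risks | No | Not triggered | Nothing on the site's view, since every SAE is already unexpected |
| The 6.2.2 test, with no list in the protocol | Yes | Triggered | Nothing: every event is unlisted, so only relatedness selects |
| The 6.2.2 test, with a list that includes the event | No | Not triggered | Nothing: listed events have already been excluded by 6.1 |
| Condition removed from 6.1, list supplied | Yes | Triggered | Works: separates listed from unlisted SAEs |

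Two things follow. First, on each of the three readings of the present text, the filter in 6.2.2 has no work to do. It has a purpose only if SAEs can be expected, which 6.1 rules out. Second, supplying the missing list without changing 6.1 would not repair the conflict. On the third reading it would take every listed event out of the SAE definition.

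The choice of reading is in practice local. Section 6.2 directs questions on adverse-event reporting first to the clinical departmental lead and the clinician supervising the case, and the Protocol Summary gives seven sites.

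**The case against.** The strongest reply is that the document's only test of unexpectedness, in 6.2.2, is whether the protocol lists the event as expected. The available text has no such list. If that test governs 6.1 as well, every event is unexpected and nothing drops out. This is a fair reading, and it rules out saying flatly that recognised complications are not SAEs. It does not remove the problem. Section 6.1 does not refer to that test, a site could reasonably use the ordinary sense of the word, and the reading works only while the list that 6.2.2 presupposes is absent.

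A second reply is that the intent is clear. Section 6.2.2 sends all SAEs to the Sponsor and a subset to the ethics committee, and its exemptions do not mention complications of ablation. The intent probably was to capture every serious event. That supports correcting 6.1, because sites classify events by the definition as written.

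Three stronger conclusions are tempting, and the documents do not support them:

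- **That expected serious events disappear from the record.** They remain adverse events under 6.1, section 6.2 says that all of these are reported, and section 8 calls for the complete dataset on every randomised patient.
- **That a comparison of safety between the mapping strategies is compromised.** None is planned. Section 3 has no safety endpoint, section 4 lists no adverse-event variable, and section 7 specifies no safety analysis.
- **That a known number or share of events is affected.** The documents give no complication rate, so no count can be derived.

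The statement that there is no list also has a limit. Some pages and a figure within 6.2.2 were not available for this review, so a list could be there. The conflict between the two sections would remain.

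**Conclusion.** The point holds as a conflict between two sections, with a real consequence on the literal reading. Section 6.1 says that an SAE must be unexpected, and section 6.2.2 makes sense only if some SAEs are expected. Where a site judges expectedness for itself, a serious complication that it regards as a known risk need not reach the Chief Investigator within 24 hours, need not receive an opinion on relatedness, and need not be notified to the Sponsor. Different sites may classify the same event differently.

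The effect is confined to prompt safety oversight. The primary endpoint, the secondary endpoints, the sample size and the planned comparisons are unchanged. The conclusion rests on two assumptions: that sites apply 6.1 as worded, and that no cross-reference or list in the unavailable material ties 6.1 to the test in 6.2.2. It does not depend on any complication rate.

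**What to change.** - **Section 6.1:** delete the two words *and unexpected* from the SAE definition, so that seriousness depends only on the listed outcomes and the existing medical-judgement paragraph.
- **Section 6.2.2:** keep expectedness here only, as the filter for the 15-day report to the ethics committee. Add to the protocol the list of expected events that this filter already refers to, and cross-refer to it.

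Make both changes together, since the list alone could widen the gap. The deletion is the essential part, and the list makes the ethics-committee filter usable.

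The cost is a short protocol amendment, a note to the sites and a few more SAE forms. Recruitment, randomisation, endpoints and analysis are not affected.

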6.2 REPORTING PROCEDURES

All adverse events will be reported. Depending on the nature of the event the reporting procedures below will be followed. As the patients are undergoing clinically indicated procedures any questions concerning adverse event reporting will be directed to the main clinical departmental lead and clinician supervising the case in the first instance.

6.2.1 Non serious AEs

All such events, whether expected or not, will be recorded.

6.2.2 Serious AEs

A SAE form should be completed and faxed to the Chief Investigator within 24 hours. However, relapse and death due to non-cardiac conditions, and hospitalisations for elective treatment of a pre-existing condition do not need reporting as SAEs.

[figure not shown]
All SAEs should be reported to the <name of REC> where in the opinion of the Chief Investigator, the event was:

'related', ie resulted from the administration of any of the research procedures; and unexpected', ie an event that is not listed in the protocol as an expected occurrence reports of related and unexpected SAEs should be submitted within 15 days of the Chief Investigator becoming aware of the event, using the NRES SAE form for non-IMP studies. The Chief Investigator must also notify the Sponsor of all SAEs.

Local investigators should report any SAEs as required by their Local Research Ethics Committee, Sponsor and/or Research & Development Office.

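### Section 6.2.2 exempts non-cardiac deaths from SAE reporting with no relatedness condition, so a death after the procedure can miss the 24-hour form and the Chief Investigator's opinion

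*Combined protocol and SAP*

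**What the plan says.** Section 6.1 of the combined protocol and SAP defines a serious adverse event as an untoward and unexpected occurrence that meets one of a list of outcomes. The first is "Results in death", with no limit by cause.

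Section 6.2.2 sets the reporting route: "A SAE form should be completed and faxed to the Chief Investigator within 24 hours". The next sentence carves out exceptions: "relapse and death due to non-cardiac conditions, and hospitalisations for elective treatment of a pre-existing condition do not need reporting as SAEs".

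The same section then says which SAEs go to the ethics committee: those "where in the opinion of the Chief Investigator, the event was" both related, meaning that it "resulted from the administration of any of the research procedures", and unexpected. Such reports are due within 15 days of the Chief Investigator becoming aware of the event. Two further sentences follow: "The Chief Investigator must also notify the Sponsor of all SAEs", and "Local investigators should report any SAEs as required by their Local Research Ethics Committee, Sponsor and/or Research & Development Office".

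Section 6.2 opens with a general statement, "All adverse events will be reported", and refers to the procedures set out beneath it.

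**The concern.** The exemption and the later assessment apply different tests. The exemption asks whether the death was cardiac. The Chief Investigator is asked whether it resulted from a research procedure and was unexpected. A death can be non-cardiac and still raise the second question. Section 2.3.1 shows how: the procedure may be done under sedation or general anaesthesia, and it involves trans-oesophageal echo and periprocedural anticoagulation. A fatal event linked to one of these could reasonably be classed as non-cardiac.

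Because the exemption removes the need for a form, it can take effect before the Chief Investigator has seen the case. What is at stake is timely central review of the most serious outcome: the relatedness opinion, any ethics-committee report that depends on it, and the Chief Investigator's own notice to the Sponsor. Section 3.2 requires no long-term data, so the deaths the trial is best placed to learn of are those close to the procedure, where relatedness is most in question.

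**Working it through.** No arithmetic applies. The check is to set the safety text side by side and look for a qualifier on the exemption, or for another route that would do the work of the form.

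1. **Is death serious whatever its cause?** Yes, under 6.1, if the occurrence was untoward and unexpected. Cause is not a condition.
2. **Does the exemption carry a relatedness condition?** No. It refers only to cause, with no exception for deaths linked to the procedure and no time window. The phrase on relapse and death can be parsed in more than one way, but non-cardiac death is exempt on each reading.
3. **Who decides that a death is non-cardiac?** The text does not say.
4. **Where is relatedness judged?** Only later in 6.2.2, by the Chief Investigator, on SAEs. The definition of related is not confined to cardiac events.
5. **Does another visible route replace the form?** Taking each in turn:
   - *Section 6.2* has all adverse events reported, but through the procedures below it, and sends reporting questions first to the departmental lead and the supervising clinician. It gives no time limit.
   - *Section 6.2.1* provides for recording of non-serious events, which a death is not.
   - *Section 6.2.2, Sponsor sentence*: the duty covers all SAEs, but the Chief Investigator can act on it only once aware of the event.
   - *Section 6.2.2, last sentence*: local investigators report SAEs as local bodies or the Sponsor require. This may bring the death to the Sponsor, depending on requirements outside the documents. It sets no time limit and does not name the Chief Investigator.
   - *Section 8* sends all data to the co-ordination centre, with no time limit.
   - *Section 3.2* asks only for redo procedures to be reported to the trial management team.
   - *The glossary* lists a Data & Safety Monitoring Board, but the supplied text gives it no role.

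Result: in the visible text the 24-hour form is the only timed route from a site to the Chief Investigator, and the exemption can switch it off for a death classed as non-cardiac. One limit applies. A figure directly after the exempting sentence is not shown, and it may describe a further route. The visible sentence does not refer to it.

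**The case against.** The strongest reply is that the sentence is being read too literally. It stands beside an exemption for elective treatment of a pre-existing condition, so the word condition most naturally means an illness, and a death from a procedural complication is due to the procedure. That is probably the intent. But the words do not impose it, and 7 sites have to apply the words.

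Second, the event is not lost. Section 6.2 calls for all adverse events to be reported, and 6.2.2 says only that these deaths need not be reported as SAEs, not that they cease to be SAEs. On that reading local reporting and the duty to notify the Sponsor still apply. This stands, and it confines the loss to timing and to an assured route to the Chief Investigator.

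Third, the effect on ethics-committee reporting may be remote. The ablation is clinically indicated, 5.1 adds no investigations beyond standard care, and 2.3.1 requires the same ablation approach in both groups. A non-cardiac death that results from a research procedure is therefore a narrow case. That is fair, but 6.2.2 gives that judgement to the Chief Investigator, who may not be asked if no form is sent.

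Fourth, removing death from the exemption goes further than adding a relatedness condition, because clearly unrelated deaths would also need a form. That is true and is a real, though small, cost. A relatedness condition alone would require someone to judge relatedness before the form is sent, and that is the difficulty to be removed.

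**Conclusion.** The point holds as a gap in reporting. As worded, a death after the procedure that is classed as non-cardiac can miss the 24-hour form, and the opinion on relatedness and expectedness may then not be given in time or at all. This rests on the visible text and on the exemption being applied as written.

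Three stronger conclusions are tempting, and the documents do not support them:

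- *That each site classifies the death for itself.* Section 6.2.2 does not say who decides. The Protocol Summary gives the number of sites and patients and nothing about classifying cause of death.
- *That the risk can be expressed as a probability over the roughly 100 patients.* The documents give no death rate, so any such figure would come wholly from an assumed one.
- *That such deaths go unrecorded, or that the trial's result is affected.* The general reporting statement in 6.2 still applies, the Sponsor may hear through local routes, and the sample size and primary analysis are unaffected.

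Nor does the point assume that a fatal complication of a clinically indicated ablation is related in the 6.2.2 sense. That is for the Chief Investigator to decide. The correction should be made because the outcome is grave and the change is small.

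**What to change.** In 6.2.2, remove death from the exempting sentence and state that every death goes to the Chief Investigator on an SAE form within 24 hours. The positive statement is useful because the 6.1 definition covers only unexpected occurrences, so deletion alone could leave some deaths in doubt. Leave the related and unexpected criteria for ethics-committee reporting as they are. If the figure not shown in 6.2.2 already requires a form for every death, bring the sentence into line with it.

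The cost is a small wording change, plus a few extra SAE forms and assessments, including some for deaths that prove unrelated. The ethics-committee criteria do not change.

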7. STATISTICS

Sample Size:

72 patients are required to have a 80% chance of detecting, as significant at the 5% level, an increase in the primary outcome measure from 50% in the control group to 80% in the experimental

group.

Our retrospective study demonstrated a diagnostic yield using RM compared to standard CARTO activation maps of 80% vs 50% (Jamil-Copley et al. 2013). Assuming the same outcome measures, this study is designed to be sufficiently large to detect a difference between arms with 80% power, at the 5% two-tailed significance level. This requires a 36 patients in each group to give a minimum sample size of 72 patients. We have elected to recruit a total of 100 patients into the study.

Categorical variables will be expressed as percentages. Continuous variables will be expressed as mean ± 1 standard deviation for parametric data and/or median ± interquartile range for non-parametric data. The 2 groups will be compared using a student's t-test for parametric data and Mann-Whitney U-Test for non-parametric data. A value of p<0.05 will be considered significant.

8. DATA MANAGEMENT AND QUALITY CONTROL

The complete dataset will be collected for all patients who are randomised into the trial. The signed, original informed consent forms and the documentation of all study procedures and assessments will be kept in the patients' study notes. All data will be transferred to the study co-ordination centre with all appropriate supporting documentation as required such as hospital reports or imaging reports with all patient identifiers removed. Patients study documents will be identified by their study-specific patient number allocated at randomisation.

9. REGULATORY ISSUES

9.1 ETHICS APPROVAL

Ethical approval for this study was granted by the NRES Committee London – Fulham on the 3rd December 2014.

The study will be conducted in accordance with the recommendations for physicians involved in research on human subjects adopted by the 18th World Medical Assembly, Helsinki 1964 and later revisions. The study must be submitted for Site Specific Assessment (SSA) at each participating NHS Trust. The Chief Investigator will require a copy of the Trust R&D approval letter before accepting participants into the study. Ethics and R&D approval

letter will be required by the Study Co-ordination Centre before accepting participants into the study.

9.2 CONSENT

Consent to enter the study will be sought from each participant only after a full explanation has been given, an information leaflet offered and time allowed for consideration. Signed participant consent will be obtained. The right of the participant to refuse to participate without giving reasons will be respected. After the participant has entered the study the clinician remains free to give alternative treatment to that specified in the protocol at any stage if he/she feels it is in the participant's best interest, but the reasons for doing so will be recorded. In these cases the participants remain within the study for the purposes of follow-up and data analysis. All participants are free to withdraw at any time from the protocol treatment without giving reasons and without prejudicing further treatment.

